6.3 Pharmacokinetic Assessments

The concentration of HC4-N by ELISA, and sperm agglutination titer in serum and endocervical mucus, and CV fluid will both be determined after each no-product baseline and product PCT cycle.

6.4 Other Assessments

An acceptability questionnaire will be administered to women and to their male partners at or within 72 hours after their product PCT cycle.

6.5 Study Visits and Procedures

Prospective participants may be pre-screened; the study will be explained, the inclusion/ exclusion criteria reviewed, questions answered, and Visit 1 scheduled.

6.5.1 Visit 1 (Screening)

- The study and informed consent form will be reviewed and all volunteer questions will be answered. If the volunteer wishes to participate and meets the preliminary study criteria, she will be asked to review and sign an informed consent form. The PI or designee will sign the form and provide a copy to the participant.
- The participant will receive an informed consent form to give to her male sexual partner. Study staff will contact him via telephone or videoconference to go over his consent form with him and answer any questions that he has. If he wants to go over the consent form in person, we will make arrangements for him to come to the clinic. The participant will bring his signed consent form in with her once he has been counseled and agrees to sign the consent. The coordinator who counseled the partner and the witness will then sign and date the consent. Visit 2 procedures will be performed after both partners have provided signatures.
- An interview will be conducted to obtain medical history, concomitant medications, and demographic information.
- A urine specimen will be obtained for a urine pregnancy test to confirm that the participant is not pregnant and to perform a urinalysis with reflex urine culture. Participants with asymptomatic bacteruria do not require antibiotic treatment, as per standard clinical practice guidelines.
- An HIV test, chemistry panel, and blood count will be performed.
- A physical exam with vital signs will be performed.
- A pelvic exam will be performed, including:
 - Signs of irritation of the external genitalia, cervix, and vagina, as observed with the naked eye will be noted.
 - A sample will be taken for wet mount and vaginal pH if indicated.
 - Specimens for *Trichomonas vaginalis, Neisseria gonorrhea* and *Chlamydia trachomatis* will be collected.
 - A Pap smear will be performed, if necessary, as consistent with standard medical practice as outlined in the study manual and inclusion criteria.
- Film insertion training:
 - The investigator or designee will explain to the participant how to insert a marketed vaginal film with similar dimensions and physical character to the ZB-06 study film (Vaginal Contraceptive Film (VCF), Apothecus Pharmaceutical Corporation). The participant will then attempt to insert a VCF film without assistance.
 - If insertion by the participant is unsuccessful, the investigator will attempt to determine what is causing the problem and will reinstruct and assist as needed. The participant may be asked to try different positions (standing, squatting,

standing with one leg raised, etc.) for insertion. If the participant can insert the film, the investigator will remove the film once proper placement is confirmed.

- If the investigator determines that the participant cannot insert the surrogate VCF correctly, then the participant will not continue in the study.
- UTI, vaginal candidiasis, and symptomatic bacterial vaginosis (BV) infections will be treated, preferably with oral medication. If the participant is otherwise eligible, she will continue in the study.
- Provided no abnormalities are found on pelvic examination, no information contained in the medical history excludes the volunteer from participating in the study, and she has demonstrated the ability to insert a surrogate film, the participant will be continued in the study.
- Participants will be given a supply of non-spermicidal, lubricated condoms for use during certain times of the study.
- The participant will be instructed to call the coordinator at the start of her next menses. At that time, the participant will be informed of the results of any laboratory tests that were not available at the enrollment visit. She will be instructed that her male partner will need to use non-lubricated condoms for any acts of intercourse after her next menses, up until approximately 72 hours prior to the cervical mucus check visit. The couple should abstain from intercourse for 72 hours prior to the predicted midcycle point.

6.5.2 Visit 2 (Enrollment)

- This visit will occur in the follicular phase of the menstrual cycle, preferably after menses ceases, on or before menstrual cycle day 10.
- Screening laboratory tests will be reviewed, along with the results of other inclusion and exclusion criteria, and eligible participants will be enrolled by entry into the Enrollment Log.
- She will be asked if there are any new or worsening medical problems or symptoms or used any medications since the last study visit. In addition, the participant will be asked if her male partner has had any adverse events (AEs) involving the urogenital system or whether he has had any serious AEs.
- She will be provided with an ovulation predictor kit (OPK) to help determine her midcycle point. Instructions for the proper use of the kit will be provided. Participants will be instructed to begin daily urine testing on day 10 of their cycle (adjusted as needed to their normal cycle length) and to contact the study coordinator if an OPK test is positive. Her mucus check visit will then be scheduled for the day of the positive test (preferred) or the next day at the latest. If the participant does not have a positive urine LH test by day 22, she will be considered anovulatory for this cycle.

- The participant will be instructed that from the start of her menses until 72 hours before her expected midcycle, she and her partner should use study-provided condoms for each act of intercourse. There should be no intercourse, use of intravaginal products (including spermicide) and her male partner should not have an ejaculation within 72 hours of expected mid-cycle date (visits 3, 6 and 9).
- 6.5.3 Visits 3, 6 and 9 (CMC Baseline [no product] Cycle, CMC ZB-06 Cycle, CMC postproduct-use safety Cycle)

This visit will be conducted on the day of ovulation or the day before or after, as determined by calculation or as identified by the presence of a positive test result with the OPK, whichever comes first.

- An interval history will be collected. Entry criteria will be reviewed to confirm the participant's eligibility.
- The participant will be asked if she has any new or worsening medical problems or symptoms or used any medications since the last study visit. In addition, she will be asked if her partner has had any AEs involving the urogenital system and whether he has had any serious AEs.
- The participant will be asked whether she refrained from intercourse and the use of intravaginal products and whether her male partner refrained from ejaculation during the previous 72 hours. If instructions were not followed, she will be reinstructed. If she used a spermicide or spermicidally lubricated condom during the previous 72 hours, the visit will be rescheduled in the next cycle. Otherwise, the visit may continue at the investigator's discretion.
- Urine will be obtained for urinalysis and reflex urine culture at visits 3 and 6.
- A urine pregnancy test will be performed at visit 6
- A blood sample (approximately 3 teaspoons) will be obtained at visits 6 and 9. The participant will undergo a pelvic exam during which a sample of cervical and vaginal secretions will be examined for midcycle characteristics and the presence of sperm. At visits 3 and 6, a colposcopy exam of the cervix and vagina will be done to determine if there are signs of irritation of the external genitalia, cervix, and vagina, as observed with the naked eye will be noted.
- Vaginal pH will be determined at visits 3 and 6. A slide for Nugent score will be obtained at visit 6
- A speculum exam will be performed and vaginal swabs, aspirate, endocervical mucus and a cervicovaginal fluid lavage (CVL) will be obtained.
- If sperm are found in the vagina or cervical mucus, the baseline cycle will be rescheduled for the following month and instructions on the use of condoms and avoidance of ejaculation will be reviewed. Longer abstinence may be recommended

for couples that have reportedly complied with the required 72-hour period. Additional supplies will be provided as needed.

- If the cervical mucus score is <10, the participant may be asked to return in 1 or 2 days if it seems likely that the midcycle point has not yet been reached, or in the next cycle if it seems likely that the midcycle point has already passed.
- If no sperm are detected at this visit, and the cervical mucus score is ≥10, the participant will be instructed to return home and have intercourse without a condom 2 to 3 hours prior to Visits 4, 7 or 10, which will be scheduled for the same or following day, within 27 hours of the mucus check visit.
- At visit 6, we will provide the participant with a ZB-06 film to use and instruct her to insert the film deep in to the vagina about 30 minutes prior to intercourse. A back up film may also be provided upon participant request or at the discretion of the investigator.
- A directed physical exam will be performed if indicated.
- The participant will be instructed to ask her partner, prior to her next visit, if he has had any AEs involving the urogenital system or whether he has had any serious AEs.
- 6.5.4 Visits 4, 7, 10 (PCT Baseline Cycle, PCT ZB-06 Cycle and post-product-use safety cycle

The participant will return to the clinic 2-3 hours after coitus ends and within 27 hours of the mucus check visit (above, visits 3, 6 and 9).

- The participant will be asked if she has any new or worsening medical problems or symptoms or used any medications since the last study visit. In addition, she will be asked if her partner has had any AEs involving the urogenital system or associated with the use of study products (as applicable) and whether he has had any serious AEs.
- A blood sample (approximately 2 teaspoons) will be obtained at visit 7.
- A wet mount or urine dipstick, or other tests, will be performed if indicated. If the test is positive for candidiasis, BV, or UTI the participant will be treated, preferably with oral medication, and continued in the study.
- Vaginal swabs or aspirate, and endocervical mucus will be obtained.
- The participant will again undergo a pelvic exam during which a sample of cervical and vaginal secretions will be evaluated for midcycle characteristics and the presence of sperm. At visits 4 and 7, a colposcopy exam of the cervix and vagina will be performed to observe if there are signs of irritation of the external genitalia, cervix, and vagina will be noted as observed with naked eye. Baseline PCT results will be interpreted and managed as listed in Appendix B.
- A directed physical exam will be performed if indicated.

- If the participant uses the study product prior to intercourse and intravaginal ejaculation cannot be achieved by the male, due to reasons such as, but not limited to: erectile dysfunction, inability to ejaculate, illness, etc., the study team will contact the sponsor and discuss if the participant may be offered a second chance at a product use cycle with a second exposure to the vaginal film, in a subsequent menstrual cycle. The participant will not present to the clinic for visit 7 in the current cycle.
- If the participant is willing and able to participate in a second product use cycle, after a failed first attempt, they will continue in the study with the intent of completing all 10 study visits.

If the participant and their partner do not want to attempt a second product use cycle, or if the sponsor does not allow this, the participant will be asked to return for visit 8 after which they will be exited from the study.

6.5.5 Visits 5 and 8 (24 hours post PCT safety checks)

- The participant will be asked if she has any new or worsening medical problems or symptoms or used any medications since the last study visit. In addition, she will be asked if her partner has had any AEs involving the urogenital system or associated with the use of study products (as applicable) and whether he has had any serious AEs.
- A colposcopy assessment will be performed
- Vaginal swabs or aspirate, endocervical mucus and a cervicovaginal fluid lavage (CVL) will be obtained.
- A blood sample (approximately two teaspoons) will be obtained.
- Urine will be obtained for urinalysis and reflex urine culture.
- Vaginal pH and slide for Nugent score will be obtained at visit 8.
- At the end of Visits 5 and 8, the participant will be given additional condoms if needed and instructed to contact the study coordinator on the first day of her next menses at which time instructions regarding sexual activity and checking urinary LH will be given. The participant will be reminded that from the start of her menses until menstrual cycle day 10, she and her partner should use study provided condoms for each act of intercourse. There should be no intercourse or use of intravaginal products (including spermicide) after menstrual cycle day 10.
- The participant will be provided with a new ovulation prediction kit. When she contacts the clinic on the first day of her next menses, she will be instructed to begin daily urine testing starting on day 10 of her cycle. She will be instructed to contact the study coordinator if a urine test result is positive. Her test cycle mucus check visit will be scheduled for the day of the positive test (preferred) or the next day at the latest. However, if she has not had a positive urine test result by day 22, she will be considered anovulatory and will either be discontinued from the study or allowed to try another cycle, depending on ZabBio, Inc. and investigator discretion.

- A wet mount or urine dipstick, or other tests, will be performed if indicated. If the test is positive for candidiasis, BV, or UTI the participant will be treated, preferably with oral medication, and continued in the study. Note that these vaginal infections may be treated with vaginal medication subsequent to 24 hr check visits.
- At visit 8, the participant will fill out an acceptability questionnaire.
- At visit 8 arrangements will be made to contact the participant's sexual partner within the next 48 hours (within approximately 72 hours from intercourse) for him to answer male acceptability questionnaire questions.

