4.2 Selection and Withdrawal of Subjects

- 4.2.1 Inclusion Criteria:
 - Age 18 50 years, inclusive
 - General good health, by volunteer history and per investigator judgment
 - History of regular menstrual cycles of 21 35 days (inclusive), by volunteer report
 - History of a normal PAP smear or ASCUS with negative HPV testing within the previous 12 months
 - Willing to abstain from intercourse and use of vaginal medications, lubricants, and other products as required in the protocol
 - Willing to use non-spermicidal, lubricated condoms for any vaginal intercourse from the first day of each menstrual cycle until 72 hours before expected midcycle
 - In a mutually monogamous relationship with a male partner who:
 - Is at least 18 years old
 - Has no known risk for sexually transmitted infections (STIs)
 - Is willing and able to comply with protocol requirements including sexual activity/ abstinence and condom use requirements
 - Can engage in vaginal intercourse with the participant, with and without condoms, as specified in protocol
 - Is not taking exogenous hormones (e.g. testosterone)
 - Protected from pregnancy by female surgical sterilization
 - Vaginal and cervical anatomy that, in the opinion of the investigator, lends itself to easy genital tract sample collection
 - Willing to give voluntary consent, sign an informed consent form and comply with study procedures as required by the protocol
- 4.2.2 Exclusion Criteria:
 - History of hysterectomy
 - Surgical sterility or known history of infertility in male partner

- Sterility or known history of sperm dysfunction in male partner
- Currently pregnant by urine pregnancy test at the enrollment visit, or within two calendar months from the last pregnancy outcome. *Note: If recently pregnant must have had at least two spontaneous menses since pregnancy outcome*
- Current use of any hormonal contraceptive or a copper or hormonal IUD, or use of Depo-Provera in the last 120 days
- Currently breastfeeding or having breastfed an infant in the last two months, or planning to breastfeed during the course of the study
- Significant gynecological abnormalities (including abnormal vaginal bleeding, excessive vaginal discharge, or vulvar/vaginal pain or irritation)
- Current UTI, vaginal candidiasis, or symptomatic bacterial vaginosis
- History of sensitivity/allergy to ZB-06 film components, for either the volunteer or her male partner

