4.4 Prior and Concomitant Medications and illnesses

Prohibited medications include use of intravaginal products within 72 hours of the expected midcycle date, as well as all hormonal contraceptives and presence of or treatment for STIs. All concomitant medications will be recorded on CRFs.

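### Section 6.5.5 starts abstinence at cycle day 10 before the product and post-product tests, section 6.5.2 starts it 72 hours before expected midcycle, and no passage reconciles the two

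*Combined protocol and SAP*

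**What the plan says.** Section 6.5.5 covers the 24-hour checks at Visits 5 and 8, so its reminder governs the cycles that follow: the product cycle (Visits 6 to 8) and the post-product cycle (Visits 9 and 10). It asks for condoms from menses to cycle day 10 and then states: "There should be no intercourse or use of intravaginal products (including spermicide) after menstrual cycle day 10". On LH testing it says "she will be instructed to begin daily urine testing starting on day 10 of her cycle". It also says that at the call on the first day of menses "instructions regarding sexual activity and checking urinary LH will be given", without saying which abstinence rule those instructions will follow.

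Other sections set the cut differently:

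- **Section 6.5.2 (Visit 2):** "from the start of her menses until 72 hours before her expected midcycle, she and her partner should use study-provided condoms". The next sentence bars intercourse, intravaginal products and partner ejaculation in that window, and ties the restriction to all three mucus checks: "her male partner should not have an ejaculation within 72 hours of expected mid-cycle date (visits 3, 6 and 9".
- **Section 4.2.1:** willingness to use condoms "from the first day of each menstrual cycle until 72 hours before expected midcycle".
- **Section 6.5.3 (Visits 3, 6 and 9):** the participant is asked about the preceding 72 hours, and that period is described as required.
- **Section 4.4:** "Prohibited medications include use of intravaginal products within 72 hours of the expected midcycle date". This concerns intravaginal products only.
- **Section 6.5.1:** "The couple should abstain from intercourse for 72 hours prior to the predicted midcycle point". This is given at screening, for the first cycle.

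**The concern.** One rule is tied to a fixed calendar day and the other to midcycle, which moves from woman to woman. The day-10 instruction is the last one written into the protocol before Visits 6 and 9. The baseline cycle has no such instruction.

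This lines up with the comparisons the trial makes. The order is fixed and non-randomized (section 4.1). Visit 4 is the comparator for Visit 7 in the primary Wilcoxon signed rank test (section 7.5.1) and for Visit 10 in the two one-sided tests of equivalence (section 7.5.3). If couples abstain for different lengths of time before the compared tests, the test conditions differ along with the use of product. With 15 evaluable couples planned, a difference in conditions that wording alone can prevent is worth removing.

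**Working it through.** The plan gives no figure on this point, so there is none to reproduce. The check is a comparison of passages plus day arithmetic.

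**Does the 72-hour rule apply beyond baseline?** Yes. Section 6.5.2 names Visits 3, 6 and 9, section 4.2.1 refers to each cycle, and section 6.5.3 applies the 72-hour question at all three mucus checks. It cannot be read as a baseline-only rule that section 6.5.5 replaces.

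**Inputs, all from section 6.5.5 unless stated:**

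- LH testing starts on cycle day 10. No positive test by day 22 means the cycle is treated as anovulatory. The positive day d therefore runs from 10 to 22, which is 13 values.
- The mucus check is on day d (preferred) or day d + 1.
- Abstinence under the day-10 instruction is counted from day 10. If day 10 itself is still open for intercourse, it is counted from day 11.
- The 72-hour rule is 3 days (sections 6.5.2 and 6.5.3).

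**Formula:** days of abstinence under section 6.5.5 alone = mucus-check day − start day. The result is compared with 3.

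| Positive day d | Check on d, from day 10: d − 10 | Check on d + 1, from day 10: d − 9 | Check on d, from day 11: d − 11 |
|---|---|---|---|
| 10 | 0 | 1 | none (check precedes day 11) |
| 11 | 1 | 2 | 0 |
| 12 | 2 | 3 | 1 |
| 13 | 3 | 4 | 2 |
| 14 | 4 | 5 | 3 |
| 22 | 12 | 13 | 11 |
| Days below 3 | 10–12 (3 of 13) | 10–11 (2 of 13) | 10–13 (4 of 13) |
| Equal to 3 | day 13 | day 12 | day 14 |
| Above 3 | 14–22 (9 of 13) | 13–22 (10 of 13) | 15–22 (8 of 13) |

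A next-day check combined with a day-11 start gives (d + 1) − 11 = d − 10, which is the first column again. Each of the two choices moves the boundary by one day, in opposite directions.

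In the main case, a couple following section 6.5.5 alone falls short of 72 hours by up to 3 days (positive test on day 10) or exceeds it by up to 12 − 3 = 9 days (positive test on day 22).

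**What catches a shortfall?** Section 6.5.3 reschedules the visit after spermicide use and when sperm are found, and lets the couple proceed only with no sperm detected and a mucus score of at least 10. Any other breach may continue at the investigator's discretion. Condom-protected intercourse inside the 72 hours may leave no sperm to detect, so a couple that kept to section 6.5.5 can fail the 72-hour question and still be tested.

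**The case against.** The strongest reply is that both rules are prohibitions, so both can be obeyed at once by following whichever starts earlier. That stands. A reader might infer that compliance with one rule forces a breach of the other, and the documents do not support that: where midcycle is late, section 6.5.5 is merely stricter than a 72-hour minimum. A short interval arises only if section 6.5.5 is followed alone, despite the Visit 2 instruction. What remains is that no passage tells couples to combine the rules, and the call on the first day of menses is not tied to either.

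It is also fair that not every section using 72 hours conflicts head-on. Section 4.4 covers intravaginal products only, section 4.2.1 is a condom-use criterion, and section 6.5.1 concerns the first cycle. The conflict rests on section 6.5.2, supported by 4.2.1 and 6.5.3.

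Section 6.5.3 limits the harm, though only in part. It also allows longer abstinence to be recommended to a couple, so a baseline cycle may run beyond 72 hours too, and longer abstinence later need not mean a difference.

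Two further inferences are tempting. One is to convert the eligible cycle lengths of 21 to 35 days into a share of women affected. The documents give no formula for midcycle and no distribution of cycle lengths, so no such share follows. The other is that the primary or equivalence comparison is biased. Nothing in the documents links days of abstinence to progressively motile sperm in endocervical mucus, so neither size nor sign can be given.

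**Conclusion.** The inconsistency is real, stands in current text, and should be corrected. On the protocol's own LH window, with a same-day mucus check and counting from day 10, section 6.5.5 alone gives less than 72 hours on 3 of 13 possible positive days, exactly 72 hours on one, and more on nine. The short days become 2 with a next-day check and 4 with a day-11 start. These are counts of calendar days, not of participants. They treat the LH-positive day as midcycle and one cycle day as 24 hours. They leave out mucus checks timed by calculation before day 10, which section 6.5.3 permits without giving a formula.

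The supported conclusion is that pre-test abstinence may differ between Visit 4 and Visits 7 and 10. A claim of bias in either comparison is not supported.

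**What to change.** Reconcile section 6.5.5 with sections 6.5.2, 4.2.1 and 6.5.3 so that the same abstinence rule applies before Visits 3, 6 and 9, and have the call on the first day of menses repeat that rule. Keep the option in section 6.5.3 of recommending longer abstinence to individual couples. Which rule applies is for the sponsor to decide.

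The cost is protocol wording and the participant instruction sheet. No visits, participants or procedures are added.
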